## 10.3 Study Period

### 10.3.1 Study Period – At-Home: Baseline Meal Challenge

#### 10.3.1.1 Visit 5: Phone, Day 0 (window of -2 day, +1 days)

The investigational center staff will:

- Remind subjects to do baseline meal challenge and to change sensor prior to starting baseline meal challenges
- Ask subjects about adverse events or device deficiencies

#### 10.3.1.2 Baseline Meal Challenges, Day 2 (window of ±2)

- Day 1:
  - Long meal with low carbohydrate count (lunch): A meal of at least 30 minutes with many bites of food (less than 5 minutes between bite) that is smaller in carbohydrates than a regular lunch meal for an individual study subject.
  - Large meal with low carbohydrate count (dinner): A large meal consists of meal that is larger in size, but smaller in carbohydrates than a regular dinner meal for an individual study subject.
- Day 2:
  - Small meal with high carbohydrate count (lunch): A large meal consists of meal that is smaller in size, but higher in carbohydrate content than a regular lunch meal for an individual study subject.
- Day 3:
  - Large drink with no carbohydrate count (breakfast)
  - Typical meal size with medium carbohydrate count (dinner): A typical meal consists one that is typical in size and carbohydrate content, i.e. a regular dinner meal for an individual study subject.
- Day 4:
  - Long meal with high carbohydrate count (lunch): A meal of at least 30 minutes with many bites of food (less than 5 minutes between bite) that is higher in carbohydrates than a regular lunch meal for an individual study subject.
- Day 5:
  - Large drink with high carbohydrate count (breakfast)

- Typical meal size with low carbohydrate count (Lunch): This typical meal consists of meal that is regular in size, but lower in carbohydrate content than a typical lunch meal for an individual study subject.

#### **10.3.1.3 Visit 6: Phone, Day 6 (window of -2 days)**

The investigational center staff will:

- Remind subject to change sensor prior to starting in-clinic meal challenges
- Ask subject about adverse events or device deficiencies

### **10.3.2 Study Period – In-Clinic: Meal Challenge**

#### **10.3.2.1 Visit 7: Start In-Clinic, Day 7 (window of +10 days)**

##### **10.3.2.1.1 Day 1**

The investigational center staff will:

- Activate automated meal gesture dosing feature in Klue Health app and confirm that system is working
- Instruct subject to eat:
  - Long meal with low carbohydrate count (lunch): A timed meal that is smaller in carbohydrates than a regular lunch meal for an individual study subject.
  - Large meal with low carbohydrate count (dinner): A large meal consists of meal that is larger in size, but smaller in carbohydrates than a regular dinner meal for an individual study subject.
- Ask subject about adverse events or device deficiencies

##### **10.3.2.1.2 Day 2**

The investigational center staff will:

- Instruct subject to eat:
  - Small meal with high carbohydrate count (lunch): A large meal consists of meal that is smaller in size, but higher in carbohydrate content than a regular lunch meal for an individual study subject.
- Ask subject about adverse events or device deficiencies

##### **10.3.2.1.3 Day 3**

The investigational center staff will:

*Medtronic Business Restricted*

- Instruct subject to eat:
  - Large drink with no carbohydrate count (breakfast)
  - Typical meal size with medium carbohydrate count (dinner): A typical meal consists one that is typical in size and carbohydrate content, i.e. a regular dinner meal for an individual study subject.
- Ask subject about adverse events or device deficiencies

#### **10.3.2.1.4 Day 4**

The investigational center staff will:

- Instruct subject to eat:
  - Typical meal size with high carbohydrate count (breakfast): This typical meal consists of meal that is regular in size, but higher in carbohydrate content than a typical breakfast meal for an individual study subject.
  - Long meal with high carbohydrate count (lunch): A timed meal that is higher in carbohydrates than a regular lunch meal for an individual study subject.
- Ask subject about adverse events or device deficiencies

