#### **7.1.2.7 FoodPrint App**

The FoodPrint app by Nutrino is a meal and event logging app. It lets the user take pictures of a meal which are synced with the food diary. FoodPrint can also be used to log activity, sleep, medications, blood glucose, and insulin. In this study, subjects will log:

- Only baseline meal challenges and activity during the at-home study period
- All meals and activity during the in-clinic study period

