#### **5 days of baseline meal challenges at home:**

- Day 1: long meal with low carb count (lunch) and large meal with low carb count (dinner)
- Day 2: small meal with high carb count (lunch)
- Day 3: large drink with no carbs (breakfast) and typical meal size with medium carb count (dinner)

*Medtronic Business Restricted*

- Day 4: long meal with high carbs (lunch)
- Day 5: large drink with high carbs (breakfast) and typical meal size with low carb count (lunch)

For the baseline meal challenges, study subjects will be asked by investigational center staff to eat a pre-defined meal, while bolusing using the pump's bolus calculator (manually announcing the meals) and logging the challenge meals in the FoodPrint app. For all other meals, subjects can consume their usual meals, but meals do not need to be logged in FoodPrint.

The Klue Health app should remain configured in monitoring-only mode during this time. The subject must wear the Apple watch on the wrist of the hand used for eating.

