#### **Study Period – 5 days (4 nights) In-Clinic:**

After the run-in period and completion of the 5-day at-home study period with baseline meal challenges, study subjects will check into the clinic for a 5-day (4 nights) intervention.

Study subjects will be asked by investigational center staff to consume meals of the same size and content they consumed for the meal challenges during the baseline meal challenge (at-home study period). For example: If a large sized dinner meal with low carbohydrate content was consumed at 5 pm on Day 1 during the baseline meal challenge, that same dinner meal should be consumed at approximately the same time on Day 1 of the in-clinic study period. Subjects will be asked by investigational center staff to check BG at the start of the meal, as well as 2 hours and 4 hours after the start of the meal and provide correction as necessary. All meals consumed during the in-clinic study period should be logged in the FoodPrint app.

Subjects will be instructed by investigational center staff to not use the pump's meal bolus calculator (no manual meal announcements) for the duration of the intervention.

Scheduled meal challenges during the study period (mirror baseline meal challenge):

- Day 1: long meal with low carb count (lunch) and large meal with low carb count (dinner)
- Day 2: small meal with high carb count (lunch)
- Day 3: large drink with no carbs (breakfast) and typical meal size with medium carb count (dinner)
- Day 4: long meal with high carbs (lunch)
- Day 5: large drink with high carb (breakfast) and typical meal size with low carb count (lunch)

On Day 5 of the in-clinic meal challenge, a subject may be asked to repeat a specific meal challenge which may require the subject to participate for an additional day.

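### In-clinic Day 4 instructs a high-carb breakfast challenge with no at-home counterpart, and because the post-prandial analyses are not limited to matched challenges, meal mix alone can shift the At-Home versus In-Clinic contrast

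*Protocol*

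**What the plan says.** The in-clinic overview in Protocol 10.1 asks subjects to "consume meals of the same size and content they consumed for the meal challenges during the baseline meal challenge" and heads its list "Scheduled meal challenges during the study period (mirror baseline meal challenge". For Day 4 that list has one entry, "Day 4: long meal with high carbs (lunch", and the at-home overview in the same section has the same single entry. The detailed at-home list in 10.3.1.2 also gives only a lunch for Day 4: "Long meal with high carbohydrate count (lunch): A meal of at least 30 minutes with many bites of food".

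The day-by-day in-clinic instruction for Day 4 (10.3.2.1.4) adds a second challenge before that lunch: "Typical meal size with high carbohydrate count (breakfast".

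On repeats, Protocol 10.1 allows a subject to be asked on in-clinic Day 5 to redo a challenge, if necessary on an extra day, and 10.3.2.1.5 has staff decide whether this is needed.

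On logging, Protocol 7.1.2.7 has subjects record "Only baseline meal challenges and activity during the at-home study period" and then "All meals and activity during the in-clinic study period". Apart from the challenges, at home "subjects can consume their usual meals, but meals do not need to be logged in FoodPrint". Table 4 in Protocol 10.4 speaks of only five baseline challenges being logged, whereas the at-home lists contain eight.

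On analysis, the primary endpoint (Protocol 5.2.1 and 14.5.1; SAP 7.9.1) is post-prandial time in range, summarised for each period. It does not say which meals count. SAP 7.9.3 adds change endpoints limited to meal challenges, a subgroup analysis by meal type, and between-period analyses of everything listed. Protocol 14.6 and SAP 7.4 put all available data into the tabulations without imputation.

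**The concern.** This is a single-arm study, so the at-home period is the only reference for gesture dosing, and the design relies on the same challenge meals being eaten in both periods. Staff cannot satisfy both the in-clinic overview and the Day 4 instruction, because there is no at-home Day 4 breakfast challenge to mirror.

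If the Day 4 instruction is followed, the in-clinic set has one more high-carb meal than the at-home set. Nothing in the analysis plan then removes it from the primary summaries or from the between-period analyses. A repeated challenge has the same effect, since it adds a second copy of one meal to the in-clinic side only. The two period figures could then differ with no effect of the device, and a reader of the report could not tell meal mix from dosing in the pooled numbers.

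**Working it through.** The documents give no sample size, power or expected time in range, so there is no figure of the plan's own to reproduce. The check counts challenges and then applies weighted-mean arithmetic.

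**Step 1. Challenges per participation.**

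| Day | At home (10.1, 10.3.1.2) | In clinic, overview (10.1) | In clinic, day by day (10.3.2.1.1 to 10.3.2.1.5) |
|---|---|---|---|
| 1 | 2 | 2 | 2 |
| 2 | 1 | 1 | 1 |
| 3 | 2 | 2 | 2 |
| 4 | 1 | 1 | 2 |
| 5 | 2 | 2 | 2 |
| Total | 8 | 8 | 9 |
| High-carb | 3 (37.5%) | 3 (37.5%) | 4 (44.4%) |

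The three high-carb challenges common to all lists are the Day 2 lunch, the Day 4 lunch and the Day 5 drink. The fourth is the Day 4 breakfast.

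**Step 2. Formula.** Let M be the mean post-prandial time in range for the other challenges, g the amount by which high-carb challenges fall below it, and p the high-carb share. With equal weight per meal, a period mean is M − p·g. If M and g are the same in both periods (no device effect), the in-clinic mean minus the at-home mean is

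shift = −(p in clinic − 3/8) × g.

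The gap g is an assumption: 10, 25 and 40 percentage points.

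**Step 3. Results.**

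| In-clinic challenges | Share difference | g = 10 | g = 25 | g = 40 |
|---|---|---|---|---|
| Overview followed, no repeat | 3/8 − 3/8 = 0 | 0 | 0 | 0 |
| Day 4 breakfast included | 4/9 − 3/8 = 5/72 | −0.69 | −1.74 | −2.78 |
| Day 4 breakfast plus one high-carb repeat | 5/10 − 3/8 = 1/8 | −1.25 | −3.12 | −5.00 |
| Overview followed, one high-carb repeat | 4/9 − 3/8 = 5/72 | −0.69 | −1.74 | −2.78 |
| Overview followed, one other repeat | 3/9 − 3/8 = −1/24 | +0.42 | +1.04 | +1.67 |

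The last two rows show that repeats matter even after the Day 4 text is corrected, and that their direction depends on which challenge is repeated.

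**Step 4. After the fix.** Restricted to challenges done in both periods, with one attempt each, a complete participation contributes 8 against 8, with 3 of 8 high-carb on both sides. The shift from this source is 0.

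**The case against.** The strongest reply is that the plan already contains much of the protection. Three of the four lists agree and the overview states the intent to mirror. The Version F entry in the version history suggests that the Day 4 breakfast is leftover text, although the conflict stands within the current sections and does not depend on that log. The change endpoints are limited to meal challenges. A challenge with no baseline has no change of its own, and with no imputation it would drop out if change were computed challenge by challenge. Subgroups by meal type are planned. The primary endpoint is only summarised for each period, and the study is unpowered and exploratory.

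Much of this stands. On its own, the Day 4 line is a text correction. But neither document says that change is computed per challenge; taken as a difference of period means, it would include the breakfast. The subgroups would expose an unmatched meal type without correcting the pooled figures. The between-period analyses cover the unrestricted summaries.

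Three stronger readings are tempting and are not supported:

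- A reader might infer that repeats have no rule at all. The general rule on available data would include them; what is missing is how they are weighted or paired.
- A reader might infer from the logging difference that all in-clinic meals would be set against eight at home. Neither document says that the meal log defines the analysed meals, and the logging text in Table 4 conflicts with the eight listed challenges, so that comparison cannot be relied on.
- A reader might infer that matched meals would isolate the effect of gesture dosing. The in-clinic overview also sets glucose checks at the start of the meal and at 2 and 4 hours, with correction as needed, and Protocol Table 5 describes constant staff surveillance in clinic. Those differences would remain.

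**Conclusion.** The point holds and should be fixed before analysis. The current text conflicts on the Day 4 in-clinic challenges, and the post-prandial contrast between periods is not restricted to matched challenges, so it can shift through meal mix alone. The extra breakfast lowers the in-clinic mean by about 0.7 to 2.8 points; with one high-carb repeat as well, by 1.25 to 5.0 points. If the overview is followed and nothing is repeated, the shift is 0.

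These sizes rest on equal weight per meal and on one common gap of 10 to 40 points for all high-carb challenges, neither of which comes from the documents. The counts of 8 and 9 do come from the documents. No error rate or success criterion is affected. The harm is limited to how the period difference is read, and the documents do not support a claim that the study's safety purpose or its data-collection objective is undermined.

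**What to change.** In the protocol, reconcile 10.3.2.1.4 with 10.1 and 10.3.1.2 so that both periods carry the same challenge list; the sponsor decides which list stands. Reconcile the logging text in Table 4, which refers to five baseline challenges, with the eight that are listed.

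In SAP 7.9.1 and 7.9.3:

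- State which meals are analysed, and base the At-Home versus In-Clinic post-prandial comparison on challenges done in both periods.
- Pair by challenge within subject and within participation, then average per subject. Pairing within participation is needed because subjects may repeat the whole study; it should also be within app release, because results are reported by release.
- Use the first attempt of a repeated challenge, unless a technical failure of a kind named in advance, and documented at the time, voids it.
- Summarise all other in-clinic meals and repeat attempts separately.

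The cost is the protocol text corrections and a few SAP sentences. The downside is that unmatched meals and repeat attempts do not enter the comparison, although they remain in the separate summaries.

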#### **10.3.2.1.5 Day 5**

The investigational center staff will:

- Instruct subject to eat:
  - Large drink with high carbohydrate count (breakfast)
  - Typical meal size with low carbohydrate count (lunch): This typical meal consists of meal that is regular in size, but lower in carbohydrate content than a typical lunch meal for an individual study subject.
- Determine if subject needs to repeat any of the meal challenges
- Ask subject about adverse events or device deficiencies
- Complete subject questionnaire
- 

#### **10.3.2.1.6 End of Study**

- Collect all study devices back from subject
- End of study

**10.3.3**

## 10.4 Data Collection/Visit Details

**Table 4. Study Visit Details**

Visit Window	Run-In Period						Study Period					End of Study	
	Visit 1 (Office)	Visit 2 (Office )	Visit 3 (Phone)	Visit 4 (Phone)	Visit 5 (Phone)	Visit 6 (Phone)	Visit 7 (Office)						
							Day 1	Day 2	Day 3	Day 4	Day 5		
Visit Activities and Data Collection													
Collect enrollment forms, e.g., Informed Consent, and forms required by local regulation	X												
Assess subject eligibility to participate in the study	X												
Measure subject height and weight Note: Body mass index (BMI) will be calculated automatically in the study database, based on height and weight measurements entered.	X												
Collect demographic and other baseline characteristics (including insulin type) according to eCRF questions	X												
Collect urine test for pregnancy from female subjects of child-bearing age or capability (Point of Care or local lab)	X												
Collect information about medical history	X												
Collect information about concomitant medications	X												
Collect/Assist with Questionnaires – Refer to Study Questionnaires Material.		X										X	
Create a new CareLink system account for the investigational center		X											
Create a CareLink Personal account for each subject and link each CareLink Personal account to the CareLink system account		X											
Set up iPhone and Apple Watch.		X											

*Medtronic Business Restricted*

**CONFIDENTIAL**

056-F275, vC Clinical Investigation Plan Template

# CIP339 Clinical Investigation Plan

D00456959

Version F

Page 45 of 93

Medtronic

Visit Window	Run-In Period						Study Period					End of Study	
	Visit 1 (Office)	Visit 2 (Office )	Visit 3 (Phone)	Visit 4 (Phone)	Visit 5 (Phone)	Visit 6 (Phone)	Visit 7 (Office)						
							Day 1	Day 2	Day 3	Day 4	Day 5		
• Set up e-mail feature on iPhone with provided e-mail address													
Set up Klue app with unique license code, refer to study material. 
 
Confirm Klue Health App is working properly (keep meal gesturing feature disabled).
 
Instruct subject to ensure that the Apple Watch is worn on the hand that is used for eating and to make sure there is no alert stating "Looking for Phone" prior to each meal.
 
		X											
Set up and train subjects on FoodPrint meal logging and meal challenges/activity. Subject will log: 
 
Only 5 baseline meal challenges and activity during the at-home study period
 
All meals and activity during the in-clinic study period
 
		X											
Train and start study subjects on the 780G system (insulin pump, CGM, MiniMed Clinical app and study meter). If available, the investigational study meter will be used. Pump settings will be as follow: 
 
Active insulin time should be set to 2 hours.
 
The pump bolus speed rate is set to Quick rate.
 
The bolus increment/step size should be set to 0.025u
 
The Carb ratio should be set to <= 40
 
The Audio settings for pump alerts should be configured to sound off and vibration on
 
		X											

Medtronic Business Restricted

CONFIDENTIAL

056-F275, vC Clinical Investigation Plan Template

# CIP339 Clinical Investigation Plan

D00456959

Version F

Page 46 of 93

Medtronic

Visit Window	Run-In Period						Study Period					End of Study	
	Visit 1 (Office)	Visit 2 (Office )	Visit 3 (Phone)	Visit 4 (Phone)	Visit 5 (Phone)	Visit 6 (Phone)	Visit 7 (Office)						
							Day 1	Day 2	Day 3	Day 4	Day 5		
Train subject on diabetes management principles, such as the treatment of hyperglycemia and hypoglycemia. In addition, there will be training regarding the need to have access to oral glucose and glucagon in case of hypoglycemia.		X											
Train subject to have back up plan in place (e.g. insulin pen or syringe) in the event they are asked to revert back to their own therapy during the study or experience study pump issues (i.e. infusion set occlusion with high glucose).		X											
Train subjects on the use of the study meter to self-monitor blood glucose (SMBG) as needed for standard of care and to make treatment decisions. Refer to user guide. 
 
If sensor glucose readings are not aligned with symptoms (e.g., if a study subject is feeling low while the sensor glucose reading is not low), use the meter to confirm blood glucose. If sensor glucose readings continue to be different from symptoms, call the study doctor
 
		X											
Train subjects on the use of ketone meter. Instruct subjects that blood ketone testing is required every time BG is greater than 300 mg/dL (16.7mmol/L), as measured by the study meter. In the event the blood ketone meter is not used to collect ketone values, urine ketones should be measured and reported.		X											

Medtronic Business Restricted

CONFIDENTIAL

056-F275, vC Clinical Investigation Plan Template

# CIP339 Clinical Investigation Plan

D00456959

Version F

Page 47 of 93

Medtronic

Visit Window	Run-In Period						Study Period					End of Study	
	Visit 1 (Office)	Visit 2 (Office )	Visit 3 (Phone)	Visit 4 (Phone)	Visit 5 (Phone)	Visit 6 (Phone)	Visit 7 (Office)						
							Day 1	Day 2	Day 3	Day 4	Day 5		
Provide guidance around paracetamol (acetaminophen): Taking medications that contain paracetamol or acetaminophen, including, but not limited to fever reducers and cold medicine, while wearing the sensor, may falsely raise sensor glucose readings and result in an over-delivery of insulin, which may cause hypoglycemia. The level of inaccuracy depends on the amount of paracetamol or acetaminophen active in the body and may be different for each person. If paracetamol or acetaminophen is taken, stop the use of the medication before using SG readings to make treatment decisions. Use additional BG meter readings to confirm glucose level		X											
Provide study subject with study meter and ketone meter, including needed supplies		X											
Complete Quality Control (QC) testing of the study meter and ketone meter per respective user guide		X											
Dispense study materials (e.g., user guides and Instructions for Subject.)		X											
Dispense other study supplies as needed (e.g., alcohol swabs, adhesive remover, etc.)		X					X						
At all visits and/or between visits (if the investigational center is contacted), adjust insulin settings and insulin dose as needed		X					X						
[REDACTED]		X (if available)					X (if available)						

Medtronic Business Restricted

CONFIDENTIAL

056-F275, vC Clinical Investigation Plan Template

# CIP339 Clinical Investigation Plan

D00456959

Version F

Page 48 of 93

Medtronic

Visit Window	Run-In Period						Study Period					End of Study	
	Visit 1 (Office)	Visit 2 (Office )	Visit 3 (Phone)	Visit 4 (Phone)	Visit 5 (Phone)	Visit 6 (Phone)	Visit 7 (Office)						
							Day 1	Day 2	Day 3	Day 4	Day 5		
Train and start study subjects on [REDACTED] upon product availability. Refer to study material.	Enrollment /Screening	Day -6 (-90 days) Start Run-In	Day -3 (-90, +2 days)	Day -1 (-1, +2 days)	Day 0 (-2, +1 days)	Day 6 (-2 days)	Day 7 (+10 days)						
Train and start study subjects on SmartGuard (Auto Mode) feature. 
 
Use the default SmartGuard target of 100mg/dL.
 
Ensure that the auto correction feature is turned ON and remains ON throughout the course of the study.
 
Instruct subjects that they should not assume that Auto Mode is able to prevent all hypoglycemia or all hyperglycemia including diabetic ketoacidosis
 
While the SmartGuard feature is active, use the temp target feature if medication containing paracetamol or acetaminophen has been taken recently. Check the label of any medication to confirm whether paracetamol or acetaminophen is an active ingredient.
 
 Auto Mode should be switched OFF in the study pump or that subjects switch to manual injections if: 
 
Hospital admission is needed for any reason
 
Glucose is persistently elevated (i.e., above 300 mg/dL [16.7 mmol/L])
 
There is an illness that prevents ingestion of fluids due to nausea and vomiting
 
		X (if available)	X (if available)	X (if available)	X (if available)	X (if available)	X (if available)	X (if available)	X (if available)	X (if available)			

Medtronic Business Restricted

CONFIDENTIAL

056-F275, vC Clinical Investigation Plan Template

